When assessing pain scores, a standardized visual analog pain scale (0-10) was used for each patient. Mean pain score on POD0 was 6.4 ± 1.3 and 6.6 ± 1.62 for the prednisolone and dexamethasone insert groups, respectively. Pain scores fell significantly on POD1 to 1.3 ± 0.45 and 2 ± 1.18 in the prednisolone and dexamethasone groups, respectively. By POD7, no patient complained of pain or discomfort (i.e., pain scale rating was “0”). No patient used ‘rescue medications’ longer than 2 days (POD0 and POD1) – the most commonly used self-reported medications were ibuprofen and acetaminophen. Seventy percent of patients in the prednisolone group vs. 60% of those patients in the dexamethasone insert group self-administered pain medications to help manage postoperative discomfort. No narcotics were prescribed or deemed necessary to help manage post-CXL pain in our study. Though not a large difference in pain scores, those in the prednisolone group reported statistically significantly lower pain scores at POD0 (t-test, $p=0.021$) and POD1 (t-test, $p=0.036$) vs. those in the dexamethasone insert group.

Ocular surface inflammation was noted to be quite mild over the course of the study. Most patients demonstrated clear conjunctiva that was free of injection by POD1; only 4 eyes (2 in the prednisolone group, 2 in dexamethasone group) had trace injection noted at time of exam. No conjunctival injection was noted at the remainder of the study visits for any subject.

Trend in intraocular pressure (IOP) was assessed from baseline to POW4. There was no significant difference in baseline IOP between groups (t-test, $p=0.518$); mean IOP was noted to be 13.5 ± 1.28 mmHg and 13.9 ± 1.64 mmHg at POD1 in prednisolone and dexamethasone insert groups, respectively. By POW4, mean IOP measured 14.25 ± 1.64 mmHg in the prednisolone

group and 13.65 ± 2.26 mmHg in the dexamethasone insert group. There was no significant rise or difference in intraocular pressure over time across both groups.

Rate of corneal re-epithelialization was assessed between groups. There was no significant difference between groups and rate of epithelial defect resolution at POD1 (t-test, $p=0.152$) and POD3 ($p=0.061$). Epithelial defect was noted to be resolved by POD7 in all subjects

Central corneal pachymetry (CCT) will often change over the course of post-CXL healing and as such was assessed at baseline and at the completion of the study between groups. As expected, there was no significant difference in mean CCT between groups at baseline (505.4 ± 47.6 μ m in prednisolone group and 509 ± 44.11 μ m in dexamethasone group), nor at POW4 (459 ± 33.89 μ m in prednisolone group; 473.15 ± 43.78 μ m in dexamethasone group).

At the end of the study, the patients were asked to complete an “ease of use” questionnaire regarding postoperative medications. The first question asked “Were directions regarding eye drop use post-CXL easy to follow”? All patients in both groups responded “yes” to this. The second question asked, “Was it cumbersome to use eye drops for more than 10 days” (this pertained to the prednisolone group), however 100% responded “no”. The final question asked “Was it difficult to remember to use postoperative drops?”; 100% of patients responded “no”. No patient experienced any adverse results in relation to treatment or CXL.

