Study variables were analyzed by appropriate statistical methods to assess for the differences between eyes treated as an entire group, and as broken down between dexamethasone implant and traditional prednisolone drop groups. Correlations between ease of use, intraocular inflammation, and epithelial healing were assessed using χ^2 , t-test, Pearson, and the Fisher Z-transformation test, evaluating the sample correlation r for significance. For independent samples, the t-test or Mann-Whitney-U test will be used for scaled data based on the outcome of the Kolmogorov-Smirnov test for normality of distribution. Ordinal data was analyzed using the Mann-Whitney-U test and chi-square or Fisher's Exact test for nominal data. P-values less than or equal to 0.05 were considered statistically significant. For non-inferiority or equivalency data, 95% confidence intervals were formulated and compared with equivalency margins. Sample size is small secondary to the incidence of the disease (1:2,000)

For any patient deciding to withdraw from the follow-up, the reasons for the withdrawal were recorded for the subsequent analysis in the interpretation of the results. Reasons behind drop out were investigated and included in study results. The authors only analyzed complete cases, as imputing the missing data using single or multiple imputation methods would be confounded by the small sample size. ITT for ease of use was calculated utilizing extremely conservative estimates of a 70% +/- 10% for drops and 90% for dexamethasone insert, while utilizing a two independent sample study with a continuous endpoint, 1:1 enrollment ratio, alpha/beta of 0.05, and power of 95%. We calculated the minimum number of patients needed to enroll as 12.

In order to account for type I errors over multiple endpoints Bonferroni adjustment method was utilized.

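### The significant day-0 pain result (t-test, p=0.021) contradicts the printed means and SDs, which give p of about 0.7

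*Combined protocol and SAP*

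**What the plan says.** The unnumbered pain paragraph of the results gives the summary statistics first: "Mean pain score on POD0 was 6.4 ± 1.3 and 6.6 ± 1.62 for the prednisolone and dexamethasone insert groups, respectively". For the next day it says: "Pain scores fell significantly on POD1 to 1.3 ± 0.45 and 2 ± 1.18 in the prednisolone and dexamethasone groups". It then draws the between-group conclusion: "those in the prednisolone group reported statistically significantly lower pain scores at POD0 (t-test, $p=0.021"), and continues with "POD1 (t-test, $p=0.036$) vs. those in the dexamethasone insert group". The same sentence concedes that the difference in scores is not large.

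On the unit of measurement, the pain paragraph says that "a standardized visual analog pain scale (0-10) was used for each patient", whereas the Biostatistics section opens with "Study variables were analyzed by appropriate statistical methods to assess for the differences between eyes treated as an entire group". Biostatistics also names the t-test or Mann-Whitney U test for independent samples, chosen by a Kolmogorov-Smirnov test, with a 0.05 threshold and a Bonferroni adjustment over multiple endpoints. The protocol summary plans 20 patients with both eyes treated. A 1:1 ratio appears in the sample size statement for ease of use.

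**The concern.** A difference of 0.2 points against SDs of 1.3 and 1.62 is about one seventh of a standard deviation. In a study of 20 patients that cannot be significant on a between-group t-test, yet the document reports it as such.

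Pain is named in the study title and is one of the evaluated outcomes. As written, a reader who takes the p-value concludes that the arms differed on the day of the procedure; a reader who takes the means and SDs concludes that no difference was shown. Anyone pooling or citing the result would get conflicting answers depending on which figures they used.

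**Working it through.** **Inputs.** Pain paragraph: POD0 6.4 (SD 1.3) against 6.6 (SD 1.62), stated p=0.021; POD1 1.3 (SD 0.45) against 2 (SD 1.18), stated p=0.036. Protocol summary: 20 patients, bilateral treatment. Biostatistics: two independent samples, 1:1.

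**Group size.** No analysed n is visible, so 10 patients (or 20 eyes) per arm is an assumption. The printed figures support it.
- The rescue-medication sentence, "Seventy percent of patients in the prednisolone group vs. 60% of those patients in the dexamethasone insert group self-administered pain medications", fits 10 per arm for both percentages: 7/10 and 6/10.
- If readings are whole numbers, the POW4 pressure mean in "13.65 ± 2.26 mmHg in the dexamethasone insert group" fits 17, 20 or 23 readings, and the insert arm's POW4 pachymetry mean of 473.15 fits 13 or 20 (counts up to 25). Only 20 fits both (273/20 and 9463/20), which is 10 patients with two eyes each.

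**POD0 from the printed figures.** With n per arm, SE = √[(1.3² + 1.62²)/n] = √(4.3144/n), t = 0.2/SE, and df = 2n − 2.

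| n per arm | SE | t | two-sided p | 95% CI for the difference |
|---|---|---|---|---|
| 10 | 0.657 | 0.304 | 0.76 | −1.18 to 1.58 |
| 20 | 0.464 | 0.431 | 0.67 | −0.74 to 1.14 |

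Welch's test gives the same p-values to two decimals. The stated 0.021 is not reproduced.

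**Attempts to reach 0.021.**
- Other sizes: p=0.82 at 6 per arm and 0.54 at 40 per arm.
- Unequal arms: the smallest two-sided p over all splits is 0.763 (20 patients) or 0.667 (40 eyes).
- Rounding, with means of 6.35 and 6.65 and SDs of 1.25 and 1.615: p=0.65 (10 per arm) or 0.52 (20 per arm).
- Best split and best rounding together: 0.645 or 0.511. Halved for a one-sided test: 0.322 or 0.256.
- SDs computed with divisor n: 0.776 or 0.677. Reading ± as a standard error: about 0.92.
- Bonferroni: adjusting a p-value can only raise it.
- Paired t-test: at best 0.08 with 10 pairs. With 20 pairs it gives 0.030 at a correlation of 0.99, so it needs a still higher one.
- Mann-Whitney U: the smallest p found over whole-number data sets of 10 per arm matching the printed means and SDs was 0.030, from contrived data.

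The last two routes would in any case make the label of a between-group t-test wrong.

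**What 0.021 would require.** The two-sided critical t is 2.529 (df 18) or 2.408 (df 38). With the printed SDs the difference would have to be 2.529 × 0.657 = 1.66 (10 per arm) or 2.408 × 0.4645 = 1.12 (20 per arm), not 0.2. With the printed difference and SDs it would take 577 per arm. A one-sided test with the most favourable rounding would still need about 193.

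**POD1.** SE = √[(0.45² + 1.18²)/n] = √(1.5949/n), and the difference is 0.7, reading the printed 2 as 2.0.

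| n per arm | t | p, Student | p, Welch | two-sided range within rounding |
|---|---|---|---|---|
| 10 | 1.75 | 0.097 | 0.106 | 0.059 to 0.162 |
| 20 | 2.48 | 0.018 | 0.020 | 0.007 to 0.045 |

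At 10 per arm the 95% CI is −0.14 to 1.54, and a one-sided test within rounding gives 0.030 to 0.081. The stated 0.036 is therefore not a two-sided patient-level t-test at 10 per arm. It is compatible with a one-sided test at 10 per arm or a two-sided test on 20 eyes per arm.

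**The case against.** The POD0 arithmetic is hard to dispute, so the best case on the other side concerns cause, scope and weight.

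- **The visit labels may be wrong.** The printed POD1 figures at 20 eyes per arm give p=0.0205 by Welch, or 0.0206 by Student if the SDs used divisor n. Either is very close to 0.021, so the p-values may have been attached to the wrong visits. This is plausible but unproven. If true, the p-value printed for POD0 is still wrong, and the POD0 claim still falls. The possibility is a good reason to check both labels against the source output.
- **Part of the text is unavailable.** A passage between Biostatistics and the pain results was not available for this review and may state group sizes or the unit of analysis. That is a fair caution against saying the document never gives them. It does not affect POD0, because no size compatible with 20 planned patients brings p near 0.021.
- **POD1 is not an error.** This stands. The value 0.036 lies within the ranges above, and POD1 is raised only as a request for clarification.
- **The consequences are small.** The text itself plays down the difference, the claim favours the comparator over the insert, and no design or analysis rule depends on it. This limits the practical effect. It does not make the reported result correct.

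**Conclusion.** The concern holds. The POD0 significance claim is wrong as written: p is 0.76 or 0.67 on the printed figures, against a stated 0.021. The 10 patients or 20 eyes per arm is an assumption, but the conclusion does not rest on it, nor on rounding, sidedness, type of SD or multiplicity adjustment. At least one of the p-value, a mean, an SD or the test label is in error, and the document does not show which.

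The must-fix rating and high confidence apply to POD0 only. For POD1, a reader cannot tell from the results sentence which analysis produced 0.036. That is a point to clarify, and the claim may stand.

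**What to change.** **POD0 (must fix).** Check the comparison against the raw data, including whether the two p-values belong to the visits they are printed with. Correct whichever of the p-value, mean, SD or test label is wrong. Report n per arm and the mean difference with its 95% CI. Withdraw the POD0 significance claim unless a printed mean, SD or the test label proves to be the misprint and the corrected analysis still supports it.

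**POD1 (verify and restate).** Rerun with the patient as the unit, since pain was scored per patient, using the plan's own rule for choosing between the t-test and Mann-Whitney U. State n, unit, sidedness, and whether p is Bonferroni-adjusted and for how many tests. Change the claim only if the patient-level result does not support it.

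**Cost.** One look-up in the source data, two reruns and one corrected sentence. The likely consequence is that the POD0 significance claim is dropped.

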11/20/2023

[figure not shown]
Dear FDA Clinical Trials Review Board,

Please find attached the *study protocol and statistical analysis plan* document as requested on the PRS System.

This is for the study: *Intracanalicular Dexamethasone Insert for Post-Corneal Cross-Linking Inflammation and Pain- The LINK Study* (IND 146603; NCT04168112)

Please do not hesitate to contact me with any questions or concerns regarding this document.
Thank you for your time and consideration.

Sincerely,

[name], DO
SightMD
[name]
[name]
[contact]

*Intracanalicular Dexamethasone Insert for Post-Corneal Cross-Linking Inflammation and Pain-
The LINK Study*

Protocol in brief: This prospective, open-label, single-center, randomized, investigator-sponsored clinical study sought to investigate the efficacy of dexamethasone intracanalicular insert on post-corneal crosslinking inflammation and pain in keratoconus patients. This study planned to enroll 20 patients and follow patients over the course of several study visits [(postoperative day (POD) 1, POD-3, POD4-7, POW2, POW3 and POW4]. It is anticipated that corneal re-epithelialization will occur within the first postoperative week, but patients were be followed closely for documentation of therapeutic effect for 30 days due to duration of steroid therapy (i.e. dexamethasone intracanalicular insert or use of Prednisolone acetate 1% ophthalmic solution tapered over 1 month in the following schedule: 4 times daily x1 week, 3 times daily x 1 week, 2 times daily x 1 week, and daily x 1 week). All patients will receive postoperative fluoroquinolone antibiotic eye drops with instructions for use (i.e. 1 drop in operative eye 4 times daily x 10 days). All patients were evaluated for pain scores, rate of corneal re-epithelialization, ease of use of the post-crosslinking regimen, and need for rescue pain medication after standard bilateral epithelium-off crosslinking.

Biostatistics

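### Bonferroni is declared without a family or multiplier, the two pain p-values called significant are not labelled as adjusted, and the POD0 value does not follow from the printed means and SDs

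*Combined protocol and SAP*

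**What the plan says.** The combined protocol and SAP has two sentences on significance, both under Biostatistics. One sets the cut-off: "P-values less than or equal to 0.05 were considered statistically significant". The other covers multiplicity: "In order to account for type I errors over multiple endpoints Bonferroni adjustment method was utilized". Neither says which endpoints form the family, how many tests are counted, or whether 0.05 applies to raw or adjusted p-values.

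Protocol in brief lists four outcomes: "All patients were evaluated for pain scores, rate of corneal re-epithelialization, ease of use of the post-crosslinking regimen, and need for rescue pain medication".

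The unnumbered results text on pain gives the summaries "Mean pain score on POD0 was 6.4 ± 1.3 and 6.6 ± 1.62 for the prednisolone and dexamethasone insert groups, respectively" and "Pain scores fell significantly on POD1 to 1.3 ± 0.45 and 2 ± 1.18 in the prednisolone and dexamethasone groups, respectively". It then states that "those in the prednisolone group reported statistically significantly lower pain scores at POD0 (t-test, $p=0.021$) and POD1 (t-test, $p=0.036", after remarking that the difference is not large. Three other between-arm p-values are printed. Two concern healing: "rate of epithelial defect resolution at POD1 (t-test, $p=0.152$) and POD3 ($p=0.061". One is a baseline check: "There was no significant difference in baseline IOP between groups (t-test, $p=0.518". None of the five is labelled raw or adjusted.

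**The concern.** A Bonferroni rule without a family cannot be applied by a reader, nor can its use be checked. This matters here because the two pain p-values lie between 0.01 and 0.05, where the multiplier decides the conclusion. They are the only between-arm differences called significant in the visible text, and they favour the comparator. If they are raw, the plan's own adjustment removes at least one of them and, for most families, both. The POD0 claim also looks odd on its face: a difference of 0.2 points with SDs of 1.3 and 1.62 in a 20-patient study would not be expected to give p=0.021.

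**Working it through.** **Inputs.** The p-values 0.021 and 0.036, the pain means and SDs, and the healing p-values 0.152 and 0.061 come from the results text. The 0.05 cut-off and the Bonferroni statement come from Biostatistics. The four outcomes and the planned 20 patients come from Protocol in brief. Analysed group sizes are not visible. Two are assumed: 10 patients per arm, or 20 eyes per arm, because treatment was bilateral.

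**Step 1: do the printed pain p-values reproduce?** Two-sample t-test with equal n: SE = √((SD₁² + SD₂²)/n), t = difference/SE, df = 2n − 2, two-sided.

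| Time | n per arm | SE | t | p |
|---|---|---|---|---|
| POD0 | 10 | √((1.69 + 2.6244)/10) = 0.657 | 0.2/0.657 = 0.304 | 0.76 |
| POD0 | 20 | √((1.69 + 2.6244)/20) = 0.464 | 0.2/0.464 = 0.431 | 0.67 |
| POD1 | 10 | √((0.2025 + 1.3924)/10) = 0.399 | 0.7/0.399 = 1.753 | 0.097 |
| POD1 | 20 | √((0.2025 + 1.3924)/20) = 0.282 | 0.7/0.282 = 2.479 | 0.0177 |

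- POD0: Welch and population-SD variants stay at 0.76 to 0.78 (n=10) and 0.67 to 0.68 (n=20). With rounding pushed to favour a difference, p is still 0.65 and 0.52. Bonferroni only raises p, so 0.021 is not reached raw or adjusted.
- POD1: the two-sided variants give 0.097 to 0.123 at n=10 (0.059 with favourable rounding) and 0.018 to 0.024 at n=20. A one-sided pooled test at n=10 gives 0.048, still not 0.036. So 0.036 is in reach only with 20 eyes per arm, although the pain score was taken once per patient.

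**Step 2: Bonferroni, if the printed values are raw.** Limit = 0.05/m; adjusted p = m × p.

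| m | Limit | POD0: m × 0.021 | POD1: m × 0.036 |
|---|---|---|---|
| 2 (the two pain times) | 0.025 | 0.042, passes | 0.072, fails |
| 3 | 0.0167 | 0.063, fails | 0.108, fails |
| 4 (outcomes in Protocol in brief) | 0.0125 | 0.084, fails | 0.144, fails |
| 5 (all between-arm p-values printed) | 0.01 | 0.105, fails | 0.180, fails |

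POD1 fails for every m ≥ 2 and POD0 for every m ≥ 3. Without adjustment, the family-wise error over four independent tests would be 1 − 0.95⁴ = 0.185. Independence is an assumption that repeated scores in the same patients are unlikely to meet.

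**Step 3: are the printed values raw?** The documents do not say, so the healing p-values were used as a check.

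- Mean IOPs of 14.25 and 13.65 and a mean corneal thickness of 473.15 fit whole-number readings on 20 eyes (14.25 × 20 = 285; 13.65 × 20 = 273; 473.15 × 20 = 9463) but not on 10.
- Assuming healing was coded yes/no in 20 eyes per arm, pooled two-sided t-tests on 7 vs 3 (or 17 vs 13) give 0.1516, and on 7 vs 2 (or 18 vs 13) give 0.0606. These match 0.152 and 0.061 with no multiplier.
- Searching all count pairs with multipliers 2 to 6, no multiplier reproduces both values. Multipliers 2 to 5 reproduce neither, and 6 reproduces only 0.061.
- Against this, the POD1 pain result at n=20 doubles to 2 × 0.0177 ≈ 0.0355, close to 0.036. Rounding in the printed means and SDs also allows a raw p of about 0.04, so the match does not settle the matter.

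**The case against.** The strongest reply is that no breach is shown. Comparing Bonferroni-adjusted p-values with 0.05 is a standard way to apply the method, so the two Biostatistics sentences can stand together. If 0.021 and 0.036 are already adjusted, calling them significant follows the rule. The healing counts appear nowhere in the documents and were found by searching for a match. Raw healing values would not prove that the pain values were handled the same way, and the doubled POD1 figure points the other way. The family is also open: with only the two pain time points, POD0 passes.

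Much of this stands. A reader might infer that the plan contains two incompatible rules, or that it demonstrably broke its own rule; the documents support neither. A reader might also infer a claim that prednisolone is better. The text says only that pain scores were lower, and calls the difference not large. Nor can the pain results simply be declared not significant, because that depends on the family and on the values being raw. A six-test family that adds IOP and corneal thickness goes beyond the four listed outcomes. The two pain results are also not the only findings called significant, since the fall in pain to POD1 is described that way too.

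The reply does not remove the need for a correction. If the values are adjusted, the family and multiplier are still missing. A doubling used for pain but not for healing would be an undeclared, selective rule. A family of two pain time points fits poorly with an adjustment stated to cover multiple endpoints. And the POD0 p-value disagrees with its own summary statistics either way.

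**Conclusion.** The concern holds in a conditional form. Certain from the text: Bonferroni is declared with no family, multiplier or adjusted threshold, and two unlabelled p-values carry the only between-arm significance claims visible. Conditional on those values being raw: POD1 fails for any family of two or more and POD0 for any of three or more. The healing p-values support raw reporting without proving it, given yes/no coding and 20 eyes per arm.

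Independent of the multiplicity question, POD0 p=0.021 is inconsistent with its printed means and SDs for 10 or 20 per arm. POD1 is below 0.05 two-sided only at the eye level (about 0.02, against about 0.10 with 10 patients per arm). These recomputations rest on the assumed group sizes. The matter goes beyond missing detail, because settling it is likely to change a stated conclusion.

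**What to change.** 1. Recompute both pain p-values from the data with the patient as the unit, and reconcile them with the printed means and SDs. This comes first, since multiplying an irreproducible 0.021 would carry the error forward.
2. In Biostatistics, state the Bonferroni family (at least the four outcomes in Protocol in brief, saying how repeated time points are counted) and its multiplier. Say that the 0.05 cut-off applies to adjusted p-values only.
3. Print raw and adjusted p-values side by side, each with the between-arm difference and its 95% confidence interval.
4. Withdraw the significance claim for any comparison whose adjusted p-value exceeds 0.05.

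The cost is a re-run of two tests on existing data, a multiplication, and edits to the analysis and results text. No new data are needed. The downside is that the pain claim probably becomes weaker.

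### Central corneal thickness (CCT) at week 4 is compared between arms without using the baseline CCT and with no interval; a post hoc patient-level ANCOVA would be more precise if the baseline correlation exceeds about 0.25.

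*Combined protocol and SAP*

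**What the plan says.** **Planned methods.** The Biostatistics section says: "For independent samples, the t-test or Mann-Whitney-U test will be used for scaled data", the choice depending on a normality test. In the text supplied it names no ANCOVA, paired or repeated-measures method for such data. It mentions intervals for one purpose only: for non-inferiority or equivalency data, "95% confidence intervals were formulated and compared with equivalency margins".

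**CCT.** The results paragraph on pachymetry explains that thickness tends to change after crosslinking and "as such was assessed at baseline and at the completion of the study between groups". It continues: "As expected, there was no significant difference in mean CCT between groups at baseline", and says the same of POW4. Means and SDs are printed for both times. There is no p value, change from baseline, adjusted difference or interval.

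**IOP.** The results paragraph on IOP says that the trend between baseline and POW4 was examined, without naming a method. It gives a between-arm p value of 0.518 at baseline, and means with SDs at POD1 and POW4. It concludes: "There was no significant rise or difference in intraocular pressure over time across both groups". The baseline means are not in the text supplied.

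One part of the combined document was not available for this review, so it could contain text that bears on this point.

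**The concern.** The reason given for measuring CCT is that it changes, so a reader wants to know whether it changed differently in the two arms. Two cross-sectional tests answer that inefficiently. The baseline test says nothing about treatment, because any difference between randomised arms at baseline is due to chance. The POW4 test leaves in its error term all the variation between patients that was already present at baseline, although the data to remove it were collected.

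A non-significant result without an interval also gives no idea of how large a difference remains possible. With about 10 patients per arm that range is wide, and a reader could take the statement as evidence that the arms are alike on thickness.

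**Working it through.** **Inputs.** From the results paragraph on pachymetry (prednisolone, then insert):
- Baseline CCT: 505.4 (SD 47.6) and 509 (SD 44.11) µm.
- POW4 CCT: 459 (SD 33.89) and 473.15 (SD 43.78) µm.

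Assumptions: 10 patients per arm (20 planned in Protocol in brief, 1:1 ratio in Biostatistics; the numbers analysed are not in the text supplied), and printed SDs taken as patient-level. The baseline-to-POW4 correlation r is not given, so a range is used. The documents state no interval or power figure for CCT, so there is none to reproduce.

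**Change from the printed means.** Prednisolone: 459 - 505.4 = -46.4 µm. Insert: 473.15 - 509 = -35.85 µm. The contrast is 10.55 µm, which is not reported.

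**Unadjusted POW4 comparison.**
- Pooled SD = sqrt((33.89² + 43.78²)/2) = 39.15.
- SE = 39.15 × sqrt(2/10) = 17.51.
- Half-width = t(18 df) × SE = 2.101 × 17.51 = 36.8 µm.
- Difference = 473.15 - 459 = 14.15 µm; 95% CI -22.6 to 50.9; p = 0.43.

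The upper limit exceeds the mean thinning seen in either arm.

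**ANCOVA.** The pooled baseline SD is sqrt((47.6² + 44.11²)/2) = 45.89 and the baseline difference is 509 - 505.4 = 3.6 µm.
- Half-width = t(17 df) × 39.15 × sqrt((1 - r²) × 18/17) × sqrt(2/10), with t(17 df) = 2.110. Including the 3.6 µm imbalance changes this by less than 0.1 µm.
- Adjusted difference = 14.15 - r × (39.15/45.89) × 3.6.

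| r | Half-width (µm) | Against 36.8 | Adjusted difference (µm) | p |
|---|---|---|---|---|
| 0 | 38.0 | +3% | 14.2 | 0.44 |
| 0.3 | 36.3 | -1% | 13.2 | 0.45 |
| 0.5 | 32.9 | -10% | 12.6 | 0.43 |
| 0.7 | 27.1 | -26% | 12.0 | 0.36 |
| 0.8 | 22.8 | -38% | 11.7 | 0.29 |
| 0.9 | 16.6 | -55% | 11.4 | 0.17 |

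Break-even: r = sqrt(1 - (2.101/2.110)² × 17/18) = 0.25. A formula that averages over chance baseline imbalance puts it at 0.26 for 20 patients, and at 0.30 if only 16 are analysed.

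**Why not a plain change score.** Its SE is the square root of the sum over arms of (SDb² + SDp² - 2r × SDb × SDp)/10, where b is baseline and p is POW4. The half-width is 40.6 µm at r = 0.5 and 26.6 µm at r = 0.8. It is worse than no adjustment below r = 45.89/(2 × 39.15) = 0.59, and wider than ANCOVA at every r in the table.

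**If the SDs are per eye.** Treatment was bilateral. With between-eye correlation c, the SD of a patient's two-eye mean is the eye SD × sqrt((1 + c)/2). The unadjusted half-width is then 36.8 × 0.707 = 26.0 µm at c = 0, 31.9 µm at c = 0.5 and 36.8 µm at c = 1. In the most favourable combination, c = 0 with r = 0.9 between patient means, the ANCOVA half-width is 16.6 × 0.707 = 11.7 µm against a difference of 11.4 µm, so the interval still just includes zero.

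**The case against.** The strongest reply is that this is a choice between valid methods. Randomisation makes the POW4 comparison unbiased. The gain depends on a correlation the documents do not give, and at r = 0.3 it is only 1%. The CCT result remains non-significant throughout. Neither CCT nor IOP is among the evaluations listed in Protocol in brief, and an adjustment added now is post hoc. All of this stands, and it is why the point is minor. What remains is that the missing interval limits interpretation whatever r is, and that the possible gain costs almost nothing.

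Three stronger readings are tempting, but the documents do not support them:

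- **That baseline IOP was ignored.** The results text says IOP was followed from baseline to POW4 and draws a conclusion about rise over time, so baseline values may well have been used. What is missing is the name of the method and a baseline-adjusted between-arm estimate.
- **That omitting intervals breaks the plan.** Biostatistics ties intervals to non-inferiority or equivalency data, and the results text claims neither for CCT or IOP. The omission is a reporting weakness.
- **That the 10.55 µm contrast shows less thinning with the insert.** No interval calculated here excludes zero.

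The eye-or-patient question is also a fair objection to the figures. If the SDs are per eye, -22.6 to 50.9 µm is the wide end of the range.

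**Conclusion.** The point holds for CCT as a minor matter of precision and reporting. The POW4 comparison shown does not use the baseline CCT and has no interval, although CCT was measured because it changes with healing. There is no bias, and no conclusion is overturned.

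The size depends on r: from about 3% wider at r = 0, through break-even near 0.25, to 38% narrower at r = 0.8. These figures assume 10 patients per arm and patient-level SDs. With per-eye SDs the unadjusted half-width lies between about 26 and 37 µm. On any of these assumptions the printed data do not show that the arms are alike on thickness; they show only that no difference was detected.

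For IOP the conclusion is narrower. The method behind the trend statement is unnamed and no adjusted between-arm estimate is shown. No adjusted IOP difference can be calculated without the baseline means. Pain, re-epithelialization and ease of use are unaffected.

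**What to change.** 1. Analyse POW4 CCT at patient level (mean of the two eyes) by ANCOVA with arm and baseline CCT. Report the adjusted between-arm difference with its 95% CI, and label it post hoc because results are already reported.
2. Apply the same model to POW4 IOP, and name the method behind the statement on rise over time.
3. State the number of patients analysed per arm and whether the printed SDs are per eye or per patient.

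The cost is a re-run on data already collected, a sentence or two of text, one degree of freedom, and an interval about 3% wider if r is near zero. Being post hoc, the result supports interpretation only.
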